6.2 Exclusion Criteria All Cohorts

Patients meeting any of the following criteria will not be permitted to enter the trial:

1. Prior therapy with anti-EGFR antibodies, anti-EGFR small molecule inhibitors or irinotecan (CPT-11)
2. Any antineoplastic agent (standard or investigational) within 4 weeks prior to C1/D1
3. Radiotherapy against target lesions within 4 weeks prior to C1/D1

NOTE: Radiotherapy for pain control against non-target lesions is allowed, as long as it does not influence bone marrow function
4. Discontinuation of prior therapy with oxaliplatin and a fluoropyrimidine due to diarrhea \geq Grade 3
5. Immunosuppressive or systemic hormonal therapy within 2 weeks prior to C1/D1 with the exception of the following allowed therapies:
 - a. Hormonal therapy (e.g., Megace) for appetite stimulation
 - b. Nasal, ophthalmic, inhaled, and topical glucocorticoid preparations
 - c. Oral replacement glucocorticoid therapy for adrenal insufficiency
 - d. Low-dose maintenance steroid/hormonal therapy for other conditions (excluding steroid tapers for brain edema/metastases/radiation)
 - e. Hormonal contraceptive therapy
6. Prophylactic use of hematopoietic growth factors within 1 week prior to C1/D1
7. Active second malignancy or history of another malignancy within the last 5 years, with the exception of:
 - a. Treated, non-melanoma skin cancers
 - b. Treated carcinoma in situ of the breast or cervix
 - c. Controlled, superficial carcinoma of the urinary bladder
 - d. T1a or b carcinoma of the prostate treated according to local standard of care, with Prostate-Specific Antigen (PSA) within normal limits for the institution
8. Known Central Nervous System (CNS) or leptomeningeal metastases not controlled by prior surgery or radiotherapy, or symptoms suggesting CNS involvement for which treatment is required

NOTE: Patients with treated CNS metastases will be eligible if they are asymptomatic, do not require corticosteroids or anticonvulsants, and have confirmation of at least stable brain disease status as assessed by 2 imaging studies performed at least 4 weeks apart with the most recent study performed within 12 weeks prior to first trial drug administration
9. Inadequate recovery from an acute toxicity associated with any prior antineoplastic therapy

NOTE: Patients with any persistent chronic toxicity of Grade 1 in severity, and persistent Grade 2 alopecia and/or neuropathy secondary to prior oxaliplatin therapy, will be considered eligible for enrollment

10. Major surgical procedure within 4 weeks prior to C1/D1 or inadequate recovery from any prior surgical procedure
11. Non-healing wounds on any part of the body
12. Patients with underlying conditions which may affect or be affected by the administration of agents in the FOLFIRI regimen. This includes
 - a. Gilbert-Meulengracht syndrome
 - b. Dihydropyrimidine dehydrogenase deficiency
13. Active thrombosis, or a history of deep vein thrombosis or pulmonary embolism, within 4 weeks prior to C1/D1; any prior thrombosis must be adequately treated and stable
14. Active uncontrolled bleeding or a known bleeding diathesis
15. Significant gastrointestinal abnormalities, including:
 - a. History of inflammatory bowel disease
 - b. Diarrhea \geq Grade 2 within 2 weeks prior to C1/D1
 - c. Requirement for intravenous alimentation
 - d. Prior surgical procedures affecting absorption
 - e. Active peptic ulcer disease
16. Patients with a significant cardiovascular disease or condition, including:
 - a. Congestive heart failure (CHF) currently requiring therapy
 - b. Class III or IV cardiovascular disease according to the New York Heart Association's (NYHA) Functional Criteria (19)
 - c. Need for antiarrhythmic medical therapy for a ventricular arrhythmia
 - d. Severe conduction disturbance (e.g., 3rd degree heart block)
 - e. Unstable angina pectoris (last episode at least 6 months prior to C1/D1)
 - f. Uncontrolled hypertension (per the Investigator's discretion)
 - g. Myocardial infarction within 6 months prior to C1/D1
17. Abnormal hematologic, renal or hepatic function as defined by the following criteria:

- a. Absolute neutrophil count (ANC) $< 1.5 \times 10^9/L$ ($1500/mm^3$)
- b. Hemoglobin ≤ 9 g/dL
- c. Platelet count $< 100 \times 10^9/L$ ($100,000/mm^3$)
- d. Serum creatinine $> 1.5 \times$ upper limit of normal (ULN) for the institution
- e. Aspartate aminotransferase (AST) $> 5 \times$ ULN for the institution
- f. Alanine aminotransferase (ALT) $> 5 \times$ ULN for the institution
- g. Total bilirubin $> 1.5 \times$ ULN for the institution
- h. Prothrombin Time (PT) as assessed by International Normalized Ratio (INR) $> 1.5 \times$ ULN for the institution
- i. Partial Thromboplastin Time (PTT) $> 1.5 \times$ ULN for the institution
18. Known history of Human Immunodeficiency Virus (HIV) infection
19. Known active hepatitis B or C virus infection
20. Any of the following within 2 weeks prior to C1/D1:
 - a. Any serious or uncontrolled infection
 - b. Any infection requiring parenteral antibiotics
 - c. Unexplained fever > 38.0 °C
21. Known or suspected hypersensitivity to any of the excipients of the Sym004 drug product
22. Any other life-threatening illness, significant organ system dysfunction, or clinically significant laboratory abnormality, which in the opinion of the Investigator, would either compromise the patient's safety or interfere with the evaluation of the safety of the trial drug
23. Any kind of disorder that compromises the ability of the patient to give written informed consent and/or to comply with trial procedures or is unwilling or unable to comply with trial requirements at the discretion of the Investigator
24. Breast feeding, or plans by the patient (or the patient's partner) to become pregnant during treatment or within 3 months after the end of treatment

6.3 Withdrawal from Trial Treatment

Sym004 and FOLFIRI may be discontinued simultaneously; Sym004 treatment may be discontinued before discontinuing FOLFIRI; or FOLFIRI may be discontinued before discontinuing Sym004 treatment.

Further, if 5-FU/FA treatment is discontinued, irinotecan/Sym004 may be administered. If irinotecan administration is discontinued, 5-FU/FA/Sym004 administration may be continued.

The visit schedule for the treatment period will apply until Sym004 and all components of FOLFIRI have been discontinued. Once this has occurred, an EOT Visit will be performed within 10 days after the decision to discontinue the last of the two; Sym004 and/or FOLFIRI.

After EOT, the patient will continue to be followed until 1 month (28 +7 days) after the last dose of Sym004/FOLFIRI, when the 1M FUP Visit must be completed.

As of Amendment 3: The visit schedule for the treatment period will apply until Sym004 has been discontinued. An EOT Visit will be performed within 10 days from the decision to withdraw treatment with Sym004, and a follow-up visit will be performed 1 month after the last administration of Sym004.

6.3.1 Withdrawal from Treatment with Sym004 and/or FOLFIRI

The patient must be withdrawn from treatment with Sym004 and/or FOLFIRI in the event of any of the following:

- A DLT considered by the Investigator to require treatment discontinuation (See [Section 9.5](#)) (dose-escalation cohorts only)
- Occurrence of an AE considered by the Investigator to require treatment discontinuation
- CTCAE Grade 4 skin toxicity (applies to Sym004 only)
- FOLFIRI-related toxicity not controlled by dose-reduction guidelines are outlined in [Table 7](#) in [Section 7.2.1.1](#) and [Appendix 2](#)
- PD, verified by CT/MRI according to RECIST v1.1 ([Appendix 1](#))
- Treatment failure not meeting the criteria for PD, but considered by the Investigator to require treatment discontinuation
- Requirement for a significant surgical procedure

NOTE: Patients requiring a minor surgical procedure (e.g., port placement, skin abscess drainage) may continue at the Investigator's discretion following discussion with the Sponsor or designee. A brief interruption in therapy may be considered
- An intercurrent illness which, in the opinion of the Investigator, would prevent completion of trial-related evaluations
- The Investigator judges it necessary due to medical reasons
- Use of prohibited concomitant medication, as defined in [Section 7.5.2](#)
- Pregnancy

- Significant deviation from the protocol or eligibility criteria. Such patients will be considered protocol violations and may be discontinued from treatment after discussion with the Sponsor
- Noncompliance with trial procedures may require discontinuation after discussion with the Sponsor
- Patient withdrawal of consent and election to discontinue treatment. (Patients may leave the trial at any time for any reason if they wish to do so, without any consequences)
- Termination of the trial by the Sponsor

6.3.2 Withdrawal from Trial

The patient must be withdrawn from trial in the event of any of the following:

- The patient withdraws consent to participate
- The Investigator judges it necessary due to medical reasons

The EOT and the 1M FUP visits should be performed to the extent possible and the Investigator should ensure any SAE is followed as described in [Section 9.3](#).

6.4 Replacement of Patients

6.4.1 Dose-Escalation Phase

Patients who do not complete Cycle 1 as defined in [Section 9.5.2](#), for reasons other than DLTs, can be replaced.

Data from these patients will be included in the safety analysis, but will not contribute to the determination of the MTD.

6.4.2 Dose-Expansion Phase

It is not planned to replace any patients in the dose-expansion phase.

7.1.4 Administration of Sym004

7.1.4.1 Treatment Schedule

This is a non-randomized, open-label trial. All patients will be allocated to the IMP, Sym004, in combination with FOLFIRI. The dose of Sym004 will vary depending upon cohort assignment.

All patients will be given iv infusions of Sym004, administered every second week (Day 1 and Day 15 of each 28 day cycle ± 2 days) through a peripheral line or indwelling catheter, and with the use of an infusion pump and an inline filter.

Sym004 is dosed according to the body weight. The allocated dose level will be confirmed in writing by Sponsor or designee on the allocation form.

For all Sym004 infusions, a complete dosing history will be recorded, i.e.:

- Total dose and volume administered
- Start and stop time of infusion
- Infusion interruption or termination and reason for such actions

7.1.4.2 Dose-Escalation Phase

During the dose-escalation phase of the trial, the following dose levels of Sym004 will potentially be evaluated in combination with FOLFIRI:

- Dose Level 1: Sym004 12 mg/kg + FOLFIRI
- Dose Level 2: Sym004 15 mg/kg + FOLFIRI
- Dose Level 3: Sym004 18 mg/kg + FOLFIRI

If the toxicity profile of Dose Level 1 indicates that this dose is not tolerated, successive lower dose levels will be explored:

- Dose Level -1: Sym004 9 mg/kg + FOLFIRI
- Dose Level -2: Sym004 9 mg/kg (loading dose) + FOLFIRI followed by 6 mg/kg + FOLFIRI
- Dose Level -3: Sym004 6 mg/kg + FOLFIRI

If Sym004 at 9 mg/kg + FOLFIRI (Dose-Level -1) has not exceeded the MTD and is well tolerated during Cycle 1, but overall tolerability is judged to be insufficient to accept this dose level as the RP2D, then Dose Level -2 may be explored.

If Sym004 at 9 mg/kg + FOLFIRI (Dose-Level -1) during Cycle 1 has not exceeded the MTD, but tolerability is judged to be insufficient to accept this dose level as the RP2D, then Dose-Level -3 may be explored.

If the toxicity profile of lower doses where mandatory diarrhea prophylaxis is utilized indicates that the dose is well tolerated, further evaluation of Dose Level 1, and potentially Dose Levels 2 and 3 may take place after approval by the ISMC.

Cohorts will be filled sequentially. Patients will be allocated to the next available treatment slot within the current or next cohort, as appropriate and depending on the ongoing observation of DLTs and other safety parameters.

Each patient enrolled will receive doses of Sym004 at the allocated dose, unless dose-reduction is necessary as specified in [Section 7.1.5](#). There will be no intra-patient dose-escalation.

7.1.4.4 Dose-Expansion Phase

Once the RP2D has been determined during the dose-escalation phase, the enrollment into the dose-expansion phase will commence. All patients enrolled to this phase will be treated at the established RP2D of Sym004 in combination with FOLFIRI.

7.1.4.5 Infusion Rate for Administration of Sym004

For the first 2 Sym004 infusions (Cycle 1), the infusion rate should be increased every 30 minutes to a maximum of 400mL per hour according to the schedule shown in [Table 4](#). Thus, a maximum of 19.2 mg Sym004 will be delivered per minute per kg body weight (based on an 80 kg patient).

Table 4 Infusion Rate for Administration of Sym004

	Dose Level 4.5 mg/kg			
	Volume 250 mL, body weight 80 kg, 1.4 mg/mL			
Time - min	mL/hr	mL/30min	mg/30min	mg/min
0-30	100	50	72	2.4
31-60	150	75	108	3.6
61-90	250	125	180	6.0
Total		250 mL		

	Dose Level 6 mg/kg			
	Volume 250 mL, body weight 80 kg, 1.9 mg/mL			
Time - min	mL/hr	mL/30min	mg/30min	mg/min
0-30	100	50	96	3.2
31-60	150	75	144	4.8
61-90	250	125	240	8.0
Total		250 mL		

	Dose Level 9 mg/kg			
	Volume 500 mL, body weight 80 kg, 1.4 mg/mL			
Time - min	mL/hr	mL/30min	mg/30min	mg/min
0-30	100	50	72	2.4
31-60	200	100	144	4.8
61-90	300	150	216	7.2
91-120	400	200	288	9.6
Total		500 mL		

	Dose Level 12 mg/kg			
	Volume 500 mL, body weight 80 kg, 1.9 mg/mL			
Time - min	mL/hr	mL/30min	mg/30min	mg/min
0-30	100	50	96	3.2
31-60	200	100	192	6.4
61-90	300	150	288	9.6
91-120	400	200	384	12.8
Total		500 mL		

	Dose Level 15 mg/kg			
	Volume 500 mL, body weight 80 kg, 2.4 mg/mL			
Time - min	mL/hr	mL/30min	mg/30min	mg/min
0-30	100	50	120	4.0
31-60	200	100	240	8.0
61-90	300	150	360	12.0
91-120	400	200	480	16.0
Total		500 mL		

	Dose Level 18 mg/kg			
	Volume 500 mL, body weight 80 kg, 2.9 mg/mL			
Time - min	mL/hr	mL/30min	mg/30min	mg/min
0-30	100	50	144	4.8
31-60	200	100	288	9.6
61-90	300	150	432	14.4
91-120	400	200	576	19.2
Total		500 mL		

Abbreviations (in alphabetical order): hr, hour; min, minute

For all subsequent infusions, the infusion rate will be according to the trial site standard practices for iv administration of mAbs and no faster than the highest safest rate administered during Cycle 1.

7.1.4.6 Patient Monitoring During and After Infusion of Sym004

Patients will be treated on an outpatient basis.

Sym004 infusions should be administered under the close supervision of an experienced physician in an environment where full resuscitation facilities are immediately available. At the end of each infusion, the iv line must remain in place for at least 1 hour to allow administration of iv drugs, if necessary.

Patients will be carefully observed for a minimum of 2 hours following completion of the first administration of Sym004 and a minimum of 1 hour following completion of subsequent administrations.

7.1.4.7 Infusion-Related Reactions to Sym004

An Infusion-Related Reaction (IRR) is defined as an AE occurring during the Sym004 infusion and up to 2 hours (or longer, if considered by the Investigator to be an IRR) after the EOI, which is assessed by the Investigator to be related to the infusion of Sym004.

7.1.4.8 Handling of Infusion-Related Reactions

If an IRR occurs, it should be classified according to CTCAE and the management guidelines shown in Table 5 should be followed.

Table 5 Infusion-Related Reactions Management Guidelines

CTCAE Grade	Management/Treatment

Grade 1 Mild transient reaction; infusion interruption not indicated; intervention not indicated
	
 Continue infusion Monitor closely

Grade 2 Therapy or infusion interruption indicated but responds promptly to symptomatic treatment (e.g. antihistamines, NSAIDs, narcotics, iv fluids); prophylactic medications indicated for ≤ 24 h
	
 Interrupt Sym004 infusion for a minimum of 30 minutes. Administer symptomatic treatment (e.g. antihistamines, NSAIDs, etc.) Use supportive treatment (e.g. bronchodilator, oxygen, etc.), if necessary When symptoms have resolved and the patient is clinically stable, restart infusion at half the previous rate (when the IRR occurred) and monitor vital signs closely during the entire infusion If the vital signs remain stable and symptoms do not recur, the infusion rate can be increased at the discretion of the Investigator Monitor closely If symptoms reoccur, stop the infusion, institute remedial therapy, monitor closely and evaluate whether the patient can continue the trial

Grade 3 Prolonged (e.g., not rapidly responsive to symptomatic medication and/or brief interruption of infusion); recurrence of symptoms following initial improvement; hospitalization indicated for clinical sequelae
	
 Discontinue Sym004 infusion Administer symptomatic and supportive treatment (e.g. bronchodilator, antihistamine, glucocorticoid, iv fluid, oxygen, etc.) as needed Either withdraw the patient from treatment or continue subsequent treatments at a reduced dose Premedication should be reinstated if previously discontinued

Grade 4 Life-threatening consequences; urgent intervention indicated
	
 Stop Sym004 infusion Administer necessary life-support measures as needed Withdraw the patient from treatment

Abbreviations (in alphabetical order): CTCAE, The National Cancer Institute (NCI) Common Terminology Criteria for Adverse Events, Version 4.03; h, hours; IRR, Infusion-related Reaction; iv, intravenous; NSAID, nonsteroidal anti-inflammatory drug

7.1.5 Dose-Adjustments and Delays of Sym004

The dose of Sym004 in mg/kg, assigned to the individual patient, will be confirmed by the Sponsor or designee prior to C1/D1.

Based on the body weight of the patient, the site will calculate the nominal dose of Sym004 to be administered in mg.

Weight changes ($\geq \pm 10\%$) for a patient during trial will require recalculation of the dose ([Section 7.1.5.1](#)).

Furthermore, dose delays of Sym004 and intra-patient dose-reduction(s) may also be required upon occurrence of Grade 3 anti-EGFR-associated skin toxicity ([Section 7.1.5.2](#)) and other safety events ([Section 7.1.5.3](#)). Dose adjustments should be discussed with the Sponsor or designee prior to implementation.

If Sym004 administration is delayed, subsequent dosing will be resumed in combination with a scheduled FOLFIRI administration.

7.1.5.1 Sym004 Dose-Adjustments for Body Weight

Sym004 is dosed in mg/kg and the dose to be administered will be calculated based on the actual body weight of the patient. The dose calculated may be used for subsequent infusions, unless body weight changes $\geq \pm 10\%$ from screening, in which case the dose must be adjusted according to the change in body weight. Adjustment may be made in the event of lesser incremental changes in weight at the site's discretion.

7.1.5.2 Sym004 Dose-Modifications for Skin Toxicity

The infusion of Sym004 must be paused in the event of a Grade 3 skin toxicity, by delaying the dose of Sym004 resulting in a period of approximately 28 days between 2 Sym004 administrations.

If Sym004 is paused, all per protocol scheduled assessments must be done and FOLFIRI will be administered according to the planned schedule and [Section 7.2.1](#).

Sym004 dosing will subsequently be resumed in combination with a scheduled FOLFIRI administration and according to specific instructions on dose-delays and dose-reductions provided in [Table 6](#).

Table 6 Sym004 Dose-Reduction for Grade 3 Skin Toxicity

Skin Toxicity Grade 3	Sym004 Immediate Action	Outcome Improvement	Sym004
First occurrence	Delay dose	Yes, Grade 2	Reduce by 3 mg/kg
		Yes, Grade ≤1	Continue at same dose
		No	Discontinue
Second occurrence	Delay dose	Yes, Grade 2	Doses at 9 mg/kg or above: Reduce by 3 mg/kg Dose at 6 mg/kg: Reduce by 1.5 mg/kg
		Yes, Grade ≤1	Continue at same dose
		No	Discontinue
Subsequent occurrences	Delay dose	Yes, Grade 2	Doses at 9 mg/kg or above: Reduce by 3 mg/kg Dose at 6 mg/kg: Reduce by 1.5 mg/kg Dose at 4.5 mg/kg: Discontinue
		Yes, Grade ≤1	Continue at same dose
		No	Discontinue

In case of a Grade 2 skin toxicity, which is locally debilitating for the patient, the guidelines outlined in [Table 6](#) above may be followed at the Investigator’s discretion.

In the occurrence of fissures unresponsive to intensive therapeutic treatment as specified in [Table 15](#), the dose of Sym004 should be delayed or reduced. The need for > 2 week dose delays or dose-reduction should be discussed with the Sponsor or designee if adequate improvement is not seen after the initial delay.

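### Table 6 cuts a patient at 6 mg/kg to 3 mg/kg when a first Grade 3 skin event improves to Grade 2, because the first-occurrence row lacks the 6 mg/kg step used in the later rows

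*Protocol*

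**What the plan says.** Under protocol section 7.1.5.2, a Grade 3 skin toxicity delays Sym004, and Table 6 sets the next dose by occurrence and degree of recovery. For recovery to Grade 2 the three rows read as follows.

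- First occurrence: one instruction for all doses, "Reduce by 3 mg/kg".
- Second occurrence: a 3 mg/kg reduction at 9 mg/kg and above, and "Dose at 6 mg/kg: Reduce by 1.5 mg/kg".
- Subsequent occurrences: the same split, plus "Dose at 4.5 mg/kg: Discontinue".

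The other two outcomes are the same in every row and do not depend on dose. Recovery to Grade 1 or better keeps the dose, and no improvement ends Sym004.

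Section 7.1.4.2 makes 6 mg/kg an assignable dose in two ways: "Dose Level -3: Sym004 6 mg/kg + FOLFIRI" and "Dose Level -2: Sym004 9 mg/kg (loading dose) + FOLFIRI followed by 6 mg/kg + FOLFIRI". Section 7.1.5 asks sites to discuss Sym004 dose adjustments with the sponsor before making them.

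**The concern.** A flat 3 mg/kg reduction suits any patient whose first event comes at 9 mg/kg or more, because the result is never below 6 mg/kg. It does not suit a patient whose first event comes at 6 mg/kg. There the first-occurrence row gives a larger cut than the later rows give at the same dose, and it ends below the lowest dose that the rest of the table uses. The protocol gives no reason for a harsher step at a first event than at a second.

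The amendment log suggests how this arose. Amendment 2 added the 6 mg/kg levels, the lowest assigned level before it was 9 mg/kg, and the log lists no change to Table 6. That is only an explanation; the inconsistency lies in the current table.

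What is at stake is the dose given to an individual patient, and whether two patients at the same dose are handled alike.

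**Working it through.** **Inputs.** Reductions for recovery to Grade 2, from Table 6: first occurrence, minus 3 mg/kg at any dose; second and subsequent occurrences, minus 3 mg/kg at 9 mg/kg or above and minus 1.5 mg/kg at 6 mg/kg; subsequent occurrences, discontinue at 4.5 mg/kg. Doses, from section 7.1.4.2: 18, 15, 12, 9 and 6 mg/kg. For Dose Level -2, the 6 mg/kg path applies when the first event occurs on the 6 mg/kg maintenance dose.

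**The plan's own figure.** The lowest dose in the later rows is 6 − 1.5 = 4.5 mg/kg, which is the dose named in the discontinuation entry. The later rows are therefore consistent with each other.

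**Table 6 as written**, with every event improving to Grade 2:

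| Dose at first event (mg/kg) | Sequence |
|---|---|
| 18 | 15, 12, 9, 6, 4.5, discontinue |
| 15 | 12, 9, 6, 4.5, discontinue |
| 12 | 9, 6, 4.5, discontinue |
| 9 | 6, 4.5, discontinue |
| 6 | 3, then no entry |

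**Size at 6 mg/kg.**

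- First event: 3/6 = 50% cut, to 3 mg/kg.
- Later event: 1.5/6 = 25% cut, to 4.5 mg/kg.
- Gap: 4.5 − 3 = 1.5 mg/kg.

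A patient starting at 6 mg/kg is thus lower after one such event (3 mg/kg) than a patient starting at 9 mg/kg is after two (4.5 mg/kg).

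**What is and is not covered at 3 mg/kg.** For a further event, recovery to Grade 1 or better (continue) and no improvement (discontinue) still apply, because neither carries a dose condition. Only improvement to Grade 2 has no matching entry.

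**With both cells corrected**, the 6 mg/kg path becomes 6, 4.5, discontinue, and the other four paths do not change. Both edits are needed. As written, no path in the table above reaches 4.5 mg/kg in time for a second occurrence, so the missing stop in that row does no harm. Once the first step from 6 mg/kg is 1.5 mg/kg, a second event can occur at 4.5 mg/kg and needs an entry.

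**The case against.** The strongest case on the other side concerns reach and consequence. Dose Levels -2 and -3 were conditional, and Amendment 3 stopped enrollment. An affected patient must still be on treatment, be at 6 mg/kg, and have a first Grade 3 skin event that improves to exactly Grade 2. Sponsor discussion is asked for before any adjustment, and the error lowers the dose after toxicity rather than raising it. All of this stands and sets the rating. It does not correct the cell, since site and sponsor would consult the same row.

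A reader might infer more than the documents support.

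- *That 4.5 mg/kg is a stated minimum dose.* No sentence says so. The protocol only discontinues at 4.5 mg/kg on a subsequent occurrence. Table 4 has a panel headed "Dose Level 4.5 mg/kg", although that is not an assigned level, and none for 3 mg/kg. This makes a 4.5 mg/kg floor plausible, but it remains an inference.
- *That the missing 3 mg/kg panel leaves an infusion without a rate.* Table 4 governs early dosing: "For the first 2 Sym004 infusions (Cycle 1), the infusion rate should be increased every 30 minutes". A Grade 3 event after infusion 1 leads to about 28 days between doses, which puts infusion 2 at about Day 29, at or past the end of Cycle 1. Later infusions follow site practice, so the argument is marginal.
- *That patients cut to 6 mg/kg for other reasons are also caught.* For a Grade 3 infusion reaction, Table 5 says "Either withdraw the patient from treatment or continue subsequent treatments at a reduced dose", and section 7.1.5.3 allows a reduction for refractory hypomagnesemia. Neither gives the size of the reduction, so arrival at 6 mg/kg by these routes is possible but not laid down.
- *That section 7.1.5.2 also contradicts the Appendix 2 rule to hold 5-FU for Grade 3 or 4 skin toxicity.* Section 7.1.5.2 keeps FOLFIRI on schedule but also refers to section 7.2.1, whose subsection 7.2.1.1 leads to Appendix 2. The rules can be read as cumulative, so no contradiction is shown.

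**Conclusion.** The first-occurrence cell of Table 6 is inconsistent with the rest of the table for a patient at 6 mg/kg whose event improves to Grade 2. The cut is twice the one that the same dose receives at a later event, and one later outcome is left without an instruction. The arithmetic is certain. It assumes that the table is applied literally and, for the sequences shown, that every event improves to Grade 2.

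Severity is minor. The protocol does not say how many patients were at 6 mg/kg, so the number affected cannot be stated. The likely harm is under-dosing of an individual patient, not added toxicity. No endpoint, sample size or error rate is involved. The rule still matters for anyone continuing treatment under Amendment 3.

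**What to change.** Change two cells of Table 6, both for recovery to Grade 2.

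1. First occurrence: limit the 3 mg/kg reduction to doses of 9 mg/kg or above, and add "Dose at 6 mg/kg: Reduce by 1.5 mg/kg".
2. Second occurrence: add "Dose at 4.5 mg/kg: Discontinue".

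The cost is those two cells. Data collection and analysis do not change. Section 17 requires ethics committee approval for protocol changes, so the correction can go into the next amendment. If any continuing patient is at 6 mg/kg, the sponsor should tell that site the intended step now, through the discussion that section 7.1.5 already asks for.
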